8.8.2.1 RosaQoL

The mean change in RosaQoL subscale scores from Baseline to Weeks 12, 24, 36, 48 and 52 will be summarized using descriptive statistics.

The subscores for the RosaQoL are computed as follows:

Total Score: the unweighted mean of all RosaQoL questions

Symptom subscale score: the unweighted mean of the following symptom questions

My rosacea burns or stings (item #2)

My rosacea is irritated (item #6)

My rosacea makes my skin sensitive (item #9)

My skin feels bumpy (uneven, not smooth, irregular) (item #16)

My skin flushes (item #17)

My skin gets irritated easily (cosmetics, aftershaves, cleansers) (item #18)

My eyes bother me (feels dry or gritty) (item #19)

Functional subscale score: the unweighted mean of the following functional questions

I try to cover up my rosacea (with make-up) (item #13)

I avoid certain foods or drinks because of my rosacea (item #15)

I avoid certain environments (heat, humidity, cold) because of my rosacea (item #21)

Emotion subscale score: the unweighted mean of the following emotion questions

- I worry that my rosacea may be serious (item #1)
- I worry about getting scars from my rosacea (item #3)
- I worry that my rosacea may get worse (item #4)
- I worry about side effects from rosacea medications (item #5)
- I am embarrassed by my rosacea (item #7)
- I am frustrated by my rosacea (item #8)
- I am annoyed by my rosacea (item #10)
- I am bothered by the appearance of my skin (redness, blotchiness) (item #11)
- My rosacea makes me feel self-conscious (item #12)
- I am bothered by persistence/reoccurrence of my rosacea (item #14)
- I think about my rosacea (item #20)

Each individual item should be scored as follows: 1=Never, 2=Rarely, 3=Sometimes, 4=Often, and 5=All the time. Missing data values will not be used. If a subscale has items with missing results, the subscore and the total will not be calculated.

8.8.2.2 Rosacea Erythema and Telangiectasia Assessments

Rosacea erythema and telangiectasia assessments will be summarized at Baseline and every 4 weeks by counts and percentages. A by-subject listing will also be presented.

8.9 Safety Evaluation

8.9.1 Extent of Exposure

The extent of exposure to study product in each treatment group will be summarized by total number of days of exposure to S5G4T-1, total number of applications, number of missed applications, and number of applications the subject did not take because they were instructed not to dose. If the CRF reason for not dosing is anything but “Per Principal Investigator (PI) Instruction” it will be counted as a non-instructed missed dose. If the CRF reason for not dosing is “Per PI Instruction” it will be counted as an instructed missed dose.

The total number of days of exposure to S5G4T-1 is as follows:

Date of last documented dose of S5G4T-1 - Date of first documented dose of S5G4T-1 +1

The total number of applications taken is as follows:

Sum of: [(End date of dosing interval from the CRF – Start date of dosing interval from the CRF + 1)*Number of doses taking in dosing interval on CRF] for all dosing intervals on the CRF

The total number of non-instructed missed applications taken is as follows:

Sum of: (End date of dosing interval from the CRF with reason of “Other, specify reason” – Start date of dosing interval from the CRF + 1) for all dosing intervals on the CRF marked with a dose of 0 and with reason of “Other, specify reason”.

The total number of instructed missed applications is as follows:

Sum of: (End date of dosing interval from the CRF with reason of “Per PI Instruction” – Start date of dosing interval from the CRF + 1) for all dosing intervals on the CRF marked with a dose of 0 and with reason of “Per PI Instruction”.

Subjects who are lost to follow-up or have a dosing record with an unknown number of doses or unknown dates of the dosing intervals will not have extent of exposure variables calculated.

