12. STUDY POPULATION

Each patient who signs an informed consent and meets Entry Criteria or Inclusion/Exclusion Criteria will be enrolled in the study. Patients will receive study product in an open-label fashion (see instructions in [Section 13.4](#)) for entire trial period (i.e., the treatment assignment, E-BPO, 5% Cream (Encapsulated Benzoyl Peroxide Cream, 5%, S5G4T-1), will be known to the patient, to study personnel, Sol-Gel personnel and its representatives.

12.1. Entry Criteria (only applies for patients entering from Phase 3, SGT-54-01 or SGT-54-02)

To be included in the study, patients must meet the following eligibility /inclusion criteria:

1. Patient must sign an Institutional Review Board (IRB) approved written informed consent for the extension study.
2. Complete 12-week or within the week 12 window time (± 4 days) of the double-blind treatment period of study SGT-54-01 or Study SGT-54-02 and missed not more than one visit of Visits 3, 4 or 5 in Study SGT-54-01 or Study SGT-54-02.
3. Patients who in the opinion of the investigator, are likely to be able to follow the restrictions of the protocol and complete the study.

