- Instruct the patient on the study product application as described in [Appendix 1](#). For new patients, pump usage shall be demonstrated by the site personnel on a sample pump at the clinic to help assure the patient understands the procedure
- Dispense the patient Instruction Sheet and Diary Card to the patient (see [Appendix 1](#) for appropriate instructions for study patients)
- Dispense cleanser and moisturizer with sunscreen
- Instruct the patient that throughout the study overexposure of the face to sunlight should be avoided. Instruct the patient to use the sunscreen provided or approved; any exposure to tanning beds must be avoided during the study
- Assign study product by using IWRS
- Dispense study product pump to patient
- Remind patient to not wear make-up to all subsequent visits
- Schedule the next study visit

13.13. On-treatment (Visit 5, 8, 11; for new patients only: 14) – week 12, 24, 36; for new patients only: 48 - Day 85, 169, 253; for new patients: 337 (± 10 days)

The following procedures will be conducted at each visit:

- Ask the patient to complete Rosacea Quality of Life (RosaQoL) questionnaire (see [Appendix 0](#))
- Observe and query the patient in a non-directive fashion about any adverse events since the previous study visit
- Query the patient about any changes in concomitant therapies since the previous study visit and update the Concomitant Therapy eCRF
- Perform the IGA described in [Section 14.1](#), rosacea erythema assessment and telangiectasia assessment described in [Sections 14.2 to 14.4](#)
- Perform Cutaneous Safety Assessment and Local Tolerability Assessment as described in [Sections 15.1 to 15.2](#)
- Perform a urine pregnancy test for all females of childbearing potential (see [Section 13.8](#))
- Perform a brief physical examination

- Review the patient's compliance with the study requirements; collect and review the Patient Diary Card
- Dispense a Diary Card to the patient
- Dispense cleanser and moisturizer with sunscreen if needed
- Record number of missed doses on the appropriate eCRF page
- Review the study product application instructions with the patient
- Collect and weigh returned study product pump
- Weigh and dispense the next pump of study product.

Remind patient to not wear make-up to all subsequent visits

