17.4. Preparation, Dispensing and Storage Instructions

The study product must be dispensed only to study patients and only at study sites specified on the form FDA 1572 by authorized personnel as required by applicable regulations and guidelines.

Study product will be dispensed according to Investigator Global Assessment at: Baseline, Weeks 4, 8, 12, 16, 20, 24, 28, 32 and 36 for patients entering from study SGT-54-01 or study SGT-54-02 and for new patients at: Baseline, Weeks 4, 8, 12, 16, 20, 24, 28, 32, 36, 40, 44 and 48. Study product will be returned at: Weeks 4, 8, 12, 16, 20, 24, 28, 32, 36 and 40 for patients entering from study SGT-54-01 or study SGT-54-02 and for new patients at: Weeks 4, 8, 12, 16, 20, 24, 28, 32, 36, 40, 44, 48 and 52. Study product weight will be documented) prior to dispensing and after return of each pump per flow chart ([Section 13.9](#) and [Section 13.10](#)).

Each Patient will be instructed on the importance of returning his or her study product at each designated visit. If a Patient does not return his or her study product, he or she will be instructed to return it at the next visit.

The study coordinator will question the patient on history of study product use since the last visit and will record any missed doses (as recorded on the patient diary) in both the source documents and the appropriate eCRF. A patient who deviates significantly from the prescribed dosage will be counseled.

Study product should be stored at room temperature 20 to 25°C (68 to 77°F). Excursions permitted between 15 to 30°C (59 to 86°F). Do not freeze or refrigerate the product.

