8.1.3 Visit Windowing

For subjects receiving S5G4T-1 in 54-01/54-02, data from 54-01/54-02 will be included in summaries of 54-07. For subjects receiving vehicle in 54-01/54-02, baseline values will be sourced from 54-01/54-02 and data from follow-up visits of 54-07 will be used in summaries. The table below details the analysis visits to be summarized and the associated visits from 54-01/54-02 or 54-07 which will be sourced for each type of subject.

Analysis Visits for Efficacy and Safety Assessments

Analysis Visit	Subjects Receiving S5G4T-1 in 54-01/54-02	Subjects Receiving vehicle in 54-01/54-02
Week 4	54-01/02 - Week 4	54-07 - Week 4
Week 8	54-01/02 - Week 8	54-07 - Week 8
Week 12	54-01/02 - Week 12	54-07 - Week 12
Week 16	54-07 - Week 4	54-07 - Week 16
Week 20	54-07 - Week 8	54-07 - Week 20
Week 24	54-07 - Week 12	54-07 - Week 24
Week 28	54-07 - Week 16	54-07 - Week 28
Week 32	54-07 - Week 20	54-07 - Week 32
Week 36	54-07 - Week 24	54-07 - Week 36
Week 40	54-07 - Week 28	54-07 - Week 40
Week 44	54-07 - Week 32	Not available
Week 48	54-07 - Week 36	Not available
Week 52	54-07 - Week 40	Not available

Data from 54-07 will be mapped to the appropriate analysis visit described above based on nominal visit indications. Data from Early Termination (ET) and unscheduled visits will be determined using analysis visit windows. The analysis visit windows for ET and unscheduled visits are presented in the following table.

SGT-54-07 Analysis Visit Windows for Efficacy and Safety Assessments

Nominal Visit	Target Study Day¹	Window (Days)
Week 4	29	22 to 42
Week 8	57	43 to 70
Week 12	85	71 to 98
Week 16	113	99 to 126
Week 20	141	127 to 154
Week 24	169	155 to 182
Week 28	197	183 to 210
Week 32	225	211 to 238
Week 36	253	239 to 266
Week 40	281	267 to 294
Week 44	309	295 to 322
Week 48	337	323 to 350
Week 52	365	351 to 378

¹ Number of days since nominal Baseline visit of 54-07

Data collected at ET and unscheduled visits prior to study day 22 will not be analyzed. Data collected at ET and unscheduled visits after study day 378 will not be included in analyses.

The definition for the study day included in each study window is defined as below:

Study Day prior to Day 1 = Visit Date – Day 1 Date

Study Day on or after Day 1 = Visit Date – Day 1 Date + 1

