8.4.1 Safety Population

All analyses will be performed using the Safety Population of the study. All patients who receive at least one confirmed dose of S5G4T-1 and have at least one assessment will be included in the Safety Population.

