Table 14.3.1.4.1: Summary of Treatment-Emergent Serious Adverse Event Characteristics (Safety Population).....	82
Table 14.3.1.4.2: Summary of Treatment-Emergent Serious Adverse Events by MedDRA System Organ Class and Preferred Term (Safety Population).....	84
Table 14.3.1.4.3: Summary of Serious Treatment-Emergent Adverse Events by Severity (Safety Population)	85
Table 14.3.1.4.4: Summary of Treatment-Emergent Serious Adverse Events by Relationship to Study Drug (Safety Population)	86
Table 14.3.1.5.1: Summary of Treatment-Emergent Serious Adverse Event Characteristics – By Period (Safety Population)	87
Table 14.3.1.5.2: Summary of Treatment-Emergent Serious Adverse Events by MedDRA System Organ Class and Preferred Term – By Period (Safety Population)	89
Table 14.3.1.5.3: Summary of Treatment-Emergent Serious Adverse Events by Severity – By Period (Safety Population)	90
Table 14.3.1.5.4: Summary of Treatment-Emergent Serious Adverse Events by Relationship to Study Drug – By Period (Safety Population).....	91
Table 14.3.1.4.1: Summary of Vital Signs (Safety Population)	92

**Table 14.0.1: Summary of Subject Completion/Discontinuation
(All Enrolled Subjects)**

	SGT-54-01/SGT-54-02 Vehicle Cream (N=xxx)	SGT-54-01/SG-54-02 E-BPO 5% Cream (N=xxx)	SGT-54-07 E-BPO 5% Cream (N=xxx)
Completed Study			
Yes	xx (xx.x%)	xx (xx.x%)	xx (xx.x%)
No	xx (xx.x%)	xx (xx.x%)	xx (xx.x%)
Reason for Discontinuation			
Adverse Event	xx (xx.x%)	xx (xx.x%)	xx (xx.x%)
Lost to Follow-Up	xx (xx.x%)	xx (xx.x%)	xx (xx.x%)
Lack of Efficacy	xx (xx.x%)	xx (xx.x%)	xx (xx.x%)
Pregnancy	xx (xx.x%)	xx (xx.x%)	xx (xx.x%)
Protocol Violation	xx (xx.x%)	xx (xx.x%)	xx (xx.x%)
Withdrawal by Subject	xx (xx.x%)	xx (xx.x%)	xx (xx.x%)
Study Terminated by Sponsor	xx (xx.x%)	xx (xx.x%)	xx (xx.x%)
Physician Decision	xx (xx.x%)	xx (xx.x%)	xx (xx.x%)
Worsening of Condition	xx (xx.x%)	xx (xx.x%)	xx (xx.x%)
Other	xx (xx.x%)	xx (xx.x%)	xx (xx.x%)

SOURCE: USERNAME\SPONSOR\PROJECT\JOBNAME (DATE, TIME)

**Table 14.0.2.1: Summary of Subject Enrollment and Evaluability
(All Enrolled Subjects)**

	SGT-54-01/SGT-54-02 Vehicle Cream (N=xxx)	SGT-54-01/SG-54-02 E-BPO 5% Cream (N=xxx)	SGT-54-07 E-BPO 5% Cream (N=xxx)
Number of Subjects Included in the Safety Population	xx (xx.x%)	xx (xx.x%)	xx (xx.x%)
Number of Subjects Excluded from the Safety Population	xx (xx.x%)	xx (xx.x%)	xx (xx.x%)
Reasons Excluded from the Safety Population ^a			
No Documented use of Study Drug	xx (xx.x%)	xx (xx.x%)	xx (xx.x%)

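### SAP 8.9.1 drops patients lost to follow-up, or with any incomplete dosing record, from every exposure summary, even when their first and last documented doses are known

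*SAP*

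**What the plan says.** **Exclusion.** SAP 8.9.1 states that "Subjects who are lost to follow-up or have a dosing record with an unknown number of doses or unknown dates of the dosing intervals" have no extent-of-exposure variables calculated. Loss to follow-up is one of the discontinuation reasons in Table 14.0.1 ("Lost to Follow-Up").

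**Definition.** The same section defines total days of exposure as "Date of last documented dose of S5G4T-1 - Date of first documented dose of S5G4T-1 +1". Applications, instructed missed applications and non-instructed missed applications are separate rows of Table 14.3.0.1.

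**Population.** SAP 8.4.1: "All patients who receive at least one confirmed dose of S5G4T-1 and have at least one assessment will be included in the Safety Population". Neither condition concerns loss to follow-up or completeness of dosing records.

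**Data collected.** The visit procedures in Protocol 13.13 to 13.15 include "Record number of missed doses on the appropriate eCRF page". Under Protocol 17.4 the coordinator "will record any missed doses (as recorded on the patient diary) in both the source documents and the appropriate eCRF". Rollover patients must "Complete 12-week or within the week 12 window time" of the parent study (Protocol 12.1), and SAP 8.1.3 adds: "For subjects receiving S5G4T-1 in 54-01/54-02, data from 54-01/54-02 will be included in summaries of 54-07".

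**Intermittent use.** Product is not dispensed at IGA 0 or 1 (Protocol 14.1; SAP 6.1 and 8.8.2).

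**Target.** The Synopsis (Study Population) wants at least 300 patients followed for 28 weeks and 100 for 52. The Synopsis (Clinical Trial Duration), Protocol 11 and SAP 6.1 express the same figures as weeks of treatment.

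**The concern.** Exposure is the main descriptive result of a long-term safety study, because it tells the reader how much drug use the safety findings rest on. The exclusion removes a patient from every exposure row because of how the patient left, or because of a single incomplete record, and not because the exposure is unknown. Loss to follow-up does not erase the doses documented before it, and an unknown interval in mid-course does not erase the first and last dose dates.

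The rule also sits awkwardly with SAP 8.1.5, which summarises non-imputed data as observed. Protocol 18.4.1 plans the exposure summary without any such exclusion, and SAP 10 does not list it as a change. The SAP says that it supersedes the protocol, so this is not a breach, but nothing explains the exclusion.

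Two smaller matters affect the same table. The row called days of exposure counts calendar time that includes instructed off-drug periods. And the 300 and 100 figures, when read as weeks of treatment, cannot be checked from any planned table.

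**Working it through.** **1. The plan's own day counts.** Visit day = 7 × week + 1: 7×12+1 = 85, 7×28+1 = 197, 7×52+1 = 365. These match the target days in SAP 8.1.3 and the period limits in SAP 8.9.2. A full 28 weeks is 196 days and 52 weeks is 364 days.

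**2. Documented span that gets no value.** Assume on-schedule visits and dosing up to the last visit attended. For a patient previously on S5G4T-1, span = 54-07 day + 84. For a patient previously on vehicle, span = 54-07 day.

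| Last 54-07 visit | Day | Prior S5G4T-1 | Prior vehicle |
|---|---|---|---|
| Baseline | 1 | 85 | none yet |
| Week 4 | 29 | 113 | 29 |
| Week 8 | 57 | 141 | 57 |
| Week 12 | 85 | 169 | 85 |
| Week 16 | 113 | 197 | 113 |
| Week 20 | 141 | 225 | 141 |
| Week 24 | 169 | 253 | 169 |
| Week 28 | 197 | 281 | 197 |
| Week 32 | 225 | 309 | 225 |
| Week 36 | 253 | 337 | 253 |

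The parent-study window of ±4 days makes the first S5G4T-1 entry 81 to 89. Patients last seen at 54-07 Week 16 or later (prior S5G4T-1) or Week 28 or later (prior vehicle) have already passed 28 weeks, 197 against 196 days. That margin is one day, so early visits would shift the crossing point.

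**3. Span against days dosed.** Let k be the number of withheld dispensings between the first and last treated stretches, and r the number of separate withheld runs. With dosing on each dispensing day and up to the next visit, days dosed = span − 28k + r.

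- 365-day span, 9 dispensings that could be withheld: k = 1 leaves 365 − 28 + 1 = 338 days (338/7 = 48.3 weeks); k = 6 leaves 198 to 201; k = 7 leaves 170 to 172.
- 281-day span (prior vehicle), 8 such dispensings: k = 3 leaves 198 to 200; k = 4 leaves 170 to 173.
- Worked case: use in Weeks 0–12, 24–28 and 48–52 gives 85 + 29 + 29 = 143 days dosed. The gaps are 83 + 139 = 222 days, and 143 + 222 = 365. The table would print 365.

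So span and days dosed disagree about reaching 52 weeks after one withheld dispensing. They disagree about 28 weeks after seven of nine (365-day span) or four of eight (281-day span).

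**4. Counts at 28 and 52 weeks.** What the planned outputs offer:

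- Table 14.3.0.1: n, mean, SD, median and range only.
- By-visit Tables 14.2.1.2, 14.2.3, 14.2.4 and 14.3.1.1: n assessed at Weeks 28 and 52 from first dose, whether or not the patient was dosing. At Weeks 44 to 52 the shells mark the prior E-BPO column as NA, whereas SAP 8.1.3 says that the vehicle group is the one without data; the overall column is filled.
- By-period adverse event tables: N is period completers plus anyone with an event in the period.
- Listing 16.2.5.2: spans by patient, but no calculated values for the excluded patients.

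**5. Number affected.** The documents give no rate. As an assumption only, 5%, 10% or 20% of about 700 would be 35, 70 or 140 patients without exposure values.

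**The case against.** The strongest reply is that dosing after the last visit is unknown for a lost patient, so a missing value is honest, while a minimum would mix truncated with complete values in one mean. That stands as a reason to label such values and to show the summary both ways. It is no reason to omit them, since using documented doses imputes nothing.

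Also correct: n against N reveals the shortfall, and the raw intervals remain in Listing 16.2.5.3, so the data are not lost from the report. The span formula is stated openly, with applications and missed applications beside it, which reduces that part to a label. Patients who clear and never restart are not overstated at all.

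A reader might infer that the plan counts nobody at 28 or 52 weeks. The by-visit tables contradict this: their n largely answers the *followed* reading. It does not answer the *of treatment* reading.

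A strict 364-day cut would also be unfair. Week 40 of 54-07 may fall on Day 271, giving 271 + 84 = 355 days, or 271 + 80 = 351 if the parent study ended on Day 81. A completer who was not dispensed product at Week 36 stops near day 337 despite full follow-up.

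**Conclusion.** The exclusion rule should be changed. It withholds a value from patients who normally have about 85 to 337 documented days (prior S5G4T-1) or 29 to 253 (prior vehicle, last seen at Weeks 4 to 36), while keeping them in the safety denominators. These ranges assume on-schedule visits and dosing to the last visit; a patient who was off product at that point has a shorter span. The span label and the absence of 28- and 52-week exposure counts are secondary.

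Two stronger readings are tempting and unsupported. The first is that adverse event rates are biased: the planned percentages do not use exposure days, so they are unaffected. The second is that mean exposure is pushed in a known direction: neither the number of patients affected nor how their exposure compares with the rest is documented.

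**What to change.** 1. Replace the exclusion sentence in SAP 8.9.1. For all treated patients, calculate the span from first to last documented dose and the application counts from documented intervals. Flag values from incomplete records as minimum exposure, report how many there are, and show the summary with and without them.
2. Relabel the span as time from first to last documented application, and show days with at least one application as its own row. The existing applications row is not an exact substitute, because its formula multiplies days by doses per day and Listing 16.2.5.3 provides for more than one dose daily.
3. Add to Table 14.3.0.1 the number of patients reaching 28 and 52 weeks, on span and on days dosed. Let the 52-week span cut-off allow for the visit windows, for example by accepting a Week 52 analysis visit completed within window. Cite the by-visit n for the *followed* reading, and reconcile the two wordings of the target.

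The cost is SAP wording and modest programming on dosing records already collected. The drawback is that some values become lower bounds and must be presented as such.

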8.9.2 Adverse Events

AEs from 54-01/02 will be included in the analysis for 54-07. All AEs that were reported as ongoing in 54-01/02 will be added into the CRF for 54-07, while AEs reported as recovered/resolved will be pulled forward programmatically into 54-07.

AEs occurring during the study will be recorded and classified on the basis of MedDRA terminology. Descriptions of AEs will include the date of onset, the date the AE ended, the severity of the AE, the relationship to study product, the action taken regarding study product usage, the action taken to treat the AE, and the outcome. All reported treatment-emergent AEs (TEAEs) will be summarized by the number of patients reporting AEs, system organ class, severity, seriousness, and relationship to study product. TEAEs are those AEs with an onset on or after the date of the first study product application. For AEs recorded in the 54-07 study if the AE is not indicated as prior to first application on the CRF then it will be considered a TEAE. AEs from 54-01/02 for subjects who received S5G4T-1 in 54-01 or 54-02 will be considered a TEAE if they were considered at TEAE in the 54-01/02 study. AEs (including ongoing) from 54-01/02 study for subjects who received vehicle in 54-01 or 54-02 will be considered pre-treatment.

AEs will be summarized by period (and total) and by severity. Each patient will be counted only once within a SOC or a Preferred Term by using the AEs with the highest severity within each category.

AEs will be summarized by period (and total) and by relationship to study product. Each patient will be counted only once within a system organ class or a preferred term by using the AEs with the greatest relationship within each category.

If relationship to study drug is reported as definitely, probably, or possible, then this is defined as related. If relationship to study drug is reported as unlikely or not related, then this is defined as unrelated.

TEAEs will be summarized in total as well as by the following periods based on time of onset in relation to date of first application of S5G4T-1, based on the definitions below. Start dates will be imputed as described in Section 8.1.5.2.

- 0-12 Weeks $0 \leq \text{onset day} \leq 85$
- >12-28 Weeks $86 \leq \text{onset day} \leq 197$
- >28-52 Weeks $198 \leq \text{onset day} \leq 365$
- >52 Weeks $\text{onset day} \geq 366$

All information pertaining to AEs noted during the study will be listed by patient, detailing verbatim given by the investigator, preferred term, system organ class, start date, stop date, severity, actions taken, and drug relatedness. The AE onset will also be shown relative (in number of days) to the day of initial application of the study product.

Serious adverse events (SAEs) will be tabulated by patient.

In addition, a list of patients who discontinued from the study and a list of patients who experienced SAEs will also be provided.

